1.1. Summary

There has been an important advance in the technology for capturing electrocardiographic signals by the Holder system in recent years. Among these advances, the following stand out: a) the miniaturization of devices; b) the possibility of capturing electrical signals by electrodes applied to the thorax without the need for cable intermediation with the recorder; c) the direct positioning of the recorder on the thoracic surface, allowing greater movement of the patient without the inconvenience of artifact records or interference in the signal line; d) possibility of transmitting electrocardiographic signals almost in real time over the computer network (internet), speeding up medical intervention in cases of high-risk arrhythmias or suspected clinical condition (syncope) being caused by such arrhythmias. No less important, it should be highlighted the speed of the preparation of the reports by the analysis software itself, which interprets the records and issues an initial report, with little or no interference from a technician or physician to edit the records. This is possible when neural networks, machine learning, and artificial intelligence are used to analyze those signals. The system in question is based on the capture of electrocardiographic recordings by Quoretech's QuoreOne recorder.

In order to reliably detect, electrocardiographic recordings obtained by QuoreOne should be compared with others already routinely used in clinical practice.

The objective of this study will be to analyze the data obtained by *QuoreOne* and compare it with those obtained by *Cardiolight* recorder analyzed by Cardios' software.

1.2. Introduction

The 24-hour ambulatory electrocardiogram, performed by the Holder system, is a procedure whose objective is to find the correlation between symptoms and possible changes in the electrocardiogram in order to establish a cause-effect relationship ¹⁻⁵. In practice, a digital recorder is connected to a cable with electrodes at its ends, which are then applied to the thoracic surface. The objective is for the electrical signal emitted by the heart to be captured and recorded in at least three channels that correspond to the electrocardiographic leads ⁶. Once captured, the signals recorded on a digital card are transferred to a computer that, by means of specific software, performs the analysis and issues a result that includes the maximum, minimum and mean heart rates, in addition to the total number of atrial and ventricular ectopic heart beats, total tachycardias and ST segment alterations and T waves. The interpretation of the electrocardiographic recordings is then carried out by a specialized technical analyst who confirms the data or corrects the information that is in disagreement. The following result is confirmed by a physician⁶.

Current systems are limited to this type of analysis, but they suffer from some limitations. These are of a technical nature related to signal capture, the dependence on electrode cables, which often limit the mobility of patients and is associated with greater risks of interference in the recording channels (50/60 Hz electrical network,

touching of clothing on the electrodes; electrode displacements, etc.)¹. Depending on the intensity and duration of these alterations, there may be a need to repeat the examination.

With the advancement of technology, new signal capture systems have been developed. The possibility of applying the recorder directly to the thoracic surface eliminated the need for electrode cables. This fact not only improved the quality of the signs, but also allowed greater patient mobility, making the test better tolerated. The possibility of sending the recorded signals over the internet speeds up their interpretation. In addition, an analysis software previously trained by neural networks allows the editing of records more quickly by issuing a pre-report, facilitating the routine of the physician who will have less work to prepare the final report. With this approach, it is expected that the more exams the system analyzes, the better its performance should be, probably reaching almost the point of minimal medical interference in the final result.

In the study, which is now proposed to be carried out at the Cardiac Arrhythmias Outpatient Clinic of the Dante Pazzanese Institute of Cardiology (IDPC), Holter recordings will be performed in about 180 consecutive patients with the two systems simultaneously, the *QuoreOne* from Quoretech (system under test) and the *Cardiolight* from Cardios (conventional 24-hour Holter-system), a system that has been on the market for more than 30 years and is widely used in the country today. This approach will allow for the comparison of *QuoreOne*'s results with those of *Cardiolight*.

1.3. Hypothesis

The initial hypothesis in this study is that the electrocardiographic recordings obtained by the two systems are comparable, thus validating the information obtained by *QuoreOne*. Therefore, the study will test the hypothesis of comparability of the *QuoreOne* system in relation to the conventional Holter system.

Figure 1 – Holter, Quoreone (Quoretech) and Cardiolight (Cardios) recorders that will be used in this study.

1.4. Objectives

1.4.1. Primary Objective:

To assess whether the detection of arrhythmias by *QuoreOne* is comparable to *Cardiolight*. Detection of the following arrhythmias will be compared: atrial fibrillation or atrial flutter, supraventricular tachycardia, ventricular tachycardia, polymorphic ventricular tachycardia or ventricular fibrillation; atrioventricular block and pauses.

1.4.2 Secondary Objective

Compare the 24-hour electrocardiographic recordings detected by both systems. The following will be included in the analysis: a) maximum, minimum and mean heart rates; b) total atrial and ventricular ectopic heart beats; c) episodes of supraventricular tachycardia, ventricular tachycardia, and pauses. In addition to these variables, the duration of the examination and the convenience of using both systems should also be compared.

2. Materials and methods

2.1. Sample

It will consist of data from Holter recordings to be performed on patients from the Electrophysiology and Cardiac Arrhythmias outpatient clinic of the Medical Section of Electrophysiology of IDPC. The sample size calculation foresees the inclusion of a minimum of 182 patients with complete data from both exams.

2.2.Inclusion Criteria

 Patients aged ≥ 18 years, with indication for continuous 24-hour electrocardiographic monitoring by 24-hour Holter at the IDPC outpatient clinic, and who agree to participate in the study by signing the free and informed consent form (ICF).

2.3. Exclusion Criteria

Patients who do not sign the informed consent form will be excluded.

2.4. Holter Device

The Holter-type cardiac monitor is a portable ambulatory electrocardiography device. It aims to monitor the electrical activity of the heart over a prolonged period, usually twenty-four hours.

For this study, the *Cardiolight* recorder from the company Cardios, the predominant equipment in the medical practice of the IDPC, and the *QuoreOne* recorder, from Quoretech, will be used, which will be submitted to comparison.

2.5. Data Collection

All exams will be performed at IDPC, the exams performed with the Cardiolight equipment will be stored both in the original file (.xcm) and in the final version of the report (.pdf). The exams performed with the QuoreOne equipment will be saved directly on the online report platform and in the final version of the report (.pdf). These files will be exported to an external hard drive and sent for tabbing. If there has been a report of symptoms by the patient, this data will be included in both files to establish the relationship between the complaint and any alteration in the electrocardiogram. The parameters will be analyzed with anonymized data from the participants.

After the Holter devices are removed, the participant will be asked to answer a questionnaire about the convenience of use and functions of the *QuoreOne* device.

3. Methodology

The exams performed by the conventional system (*Cardiolight*, Cardios) and by the *QuoreOne* system will be analyzed and the reports released by physicians from the Electrophysiology Section of the IDPC. These tests will be implemented at the same time in the same patient and for the same duration. The physicians evaluating the results of one method will be the same as the physicians evaluating the results obtained by the other method, but these will be blinded to the patients' data, making it impossible to identify that the tests being evaluated are from the same patient.

4. Statistical analysis

4.1.Descriptive Analysis

Data will be collected regarding demographic variables, underlying diseases, use of medications, and medical indication for Holter monitoring. Categorical variables will be presented with counts and percentages. Quantitative variables will be presented as means and standard deviations if normal distribution and as medians and interquartile ranges if non-Gaussian distribution. The Kolmogorov-Smirnov test will be used to evaluate the normality of the distributions of quantitative variables.

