## 2. STUDY METHODS

### 2.1. Study Design

This is a comparative, single-center study with consecutive inclusion of patients. Research participants will be included prospectively.

All exams will be performed at IDPC, the exams performed with the *Cardiolight* equipment will be stored both in the original file (.xcm) and in the final version of the report (.pdf). The exams performed with the *QuoreOne* equipment will be saved directly on the online report platform and in the final version of the report (.pdf). These files will be exported to an external hard drive and sent for tabbing. The parameters will be analyzed with anonymized data from the participants.

After the Holter devices are removed, the participant will be asked to answer a questionnaire about the convenience of use and functions of the *QuoreOne* device.

The Holter-type cardiac monitor is a portable ambulatory electrocardiography device. It aims to monitor the electrical activity of the heart over a prolonged period, usually twenty-four hours.

For this study, the *Cardiolight* recorder from the company Cardios, the predominant equipment in the medical practice of the IDPC, and the *QuoreOne* recorder, from Quoretech, will be used, which will be submitted to comparison.

The exams performed by the conventional system (*Cardiolight*, Cardios) will be analyzed and the reports released by physicians from the Electrophysiology Section of the IDPC. These tests will be implemented at the same time in the same patient and for the same duration. The physicians evaluating the results of one method will be the same as the physicians evaluating the results obtained by the other method, but these will be blinded to the patients' data, making it impossible to identify that the tests being evaluated are from the same patient.

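### Symptom reports go into both exam files read by the same physicians, and neither document withholds them until the arrhythmia call is made, so the claim that pairs cannot be recognised is not secured

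*Protocol*

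**What the plan says.** Protocol 2.5 (Data Collection) describes how the exams of both systems are stored, exported and tabulated. It then adds that, where the patient has reported symptoms, "this data will be included in both files to establish the relationship between the complaint and any alteration in the electrocardiogram".

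Protocol section 3 (Methodology) describes the reading. On timing: "These tests will be implemented at the same time in the same patient and for the same duration". On readers: "The physicians evaluating the results of one method will be the same as the physicians evaluating the results obtained by the other method". It then claims that the readers are masked to patient data and cannot link the two exams. SAP 2.1 (Study Design) repeats that claim: "but these will be blinded to the patients' data, making it impossible to identify that the tests being evaluated are from the same patient". The SAP does not carry over the symptom rule.

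On anonymisation, Protocol 2.5 says only: "The parameters will be analyzed with anonymized data from the participants". That sentence concerns the analysis of parameters. It does not say that symptom text is removed from what the readers see.

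The primary measure (Protocol 4.2, SAP 5.2) is the accuracy of QuoreOne against the conventional Holter for detecting any of six arrhythmia types. SAP 2.3 sets success as a lower 95% confidence limit above 85%, with 182 patients. SAP 5.4 adds Cohen's kappa.

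**The concern.** The primary result is the agreement between two physician readings of the same patient's simultaneous recordings. It is credible only if the second reading is made without knowledge of the first. The plan relies on masking for this, and states it in absolute terms.

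A symptom report is specific to the patient. If the same complaint appears in two files covering the same period, and the same physicians read both, the second file may be recognised. A reader who recognises it would tend to repeat the first call where the tracing leaves room for interpretation. Discordant pairs would then become concordant. Accuracy, kappa and the per-arrhythmia statistics would be expected to shift upward, and with them the chance of clearing the 85% bar.

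The six arrhythmia definitions make no use of symptoms, so the readers do not need them for the primary call.

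**Working it through.** **1. The texts side by side**

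| Question | Protocol | SAP |
|---|---|---|
| Is the symptom report in both files? | Yes, when the patient reports symptoms (2.5) | Not mentioned |
| Same physicians for both exams? | Yes (3) | Yes (2.1) |
| Can pairs be linked? | Said to be impossible (3) | Said to be impossible (2.1) |
| Symptoms withheld until the call is made? | Not stated | Not stated |
| Reading order, interval between paired readings, or split of pairs between readers? | Not stated | Not stated |

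Nothing in either document reconciles the first row with the third.

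**2. The plan's own figure**

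Inputs from the SAP 2.3 table: agreement (83 + 50)/146 = 0.911; null value 0.85; n = 182; one-sided 2.5%; power 80%.

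The SAP does not name the interval method, so two are used. With x agreements, the Wald lower limit is x/n − 1.96·√[(x/n)(1 − x/n)/n].

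- Wald: x = 162 gives 0.8447 and x = 163 gives 0.8512, so success needs at least 163 of 182. Exact binomial power at 0.911 is 80.7%, which reproduces the planned 80%.
- Exact (Clopper-Pearson): x = 164 gives 0.8482 and x = 165 gives 0.8547, so success needs at least 165 of 182.

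**3. Effect of carried-over calls (illustration)**

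Let r be the fraction of all truly discordant pairs that become concordant through recognition. Then

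apparent accuracy = 1 − (1 − true accuracy)(1 − r).

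Set true accuracy at 0.85, the boundary at which the device should not pass. Expected discordant pairs are 182 × 0.15 = 27.3. The Wald rule tolerates 182 − 163 = 19, so about 8 changed calls separate the expected count from success. P(success) is the binomial probability of reaching the cut-off at the apparent accuracy.

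| r | Apparent accuracy | Wald (≥163) | Exact (≥165) |
|---|---|---|---|
| 0 | 0.850 | 4.8% | 1.7% |
| 6% | 1 − 0.15 × 0.94 = 0.859 | 9.1% | 3.6% |
| 10% | 1 − 0.15 × 0.90 = 0.865 | 13.4% | 5.7% |

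The 4.8% at r = 0 comes from the Wald interval and has nothing to do with symptoms.

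**4. What limits r**

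This route needs a symptom report, recognition of the pair and a changed call, so r is the product of three fractions taken among discordant pairs. It cannot exceed the share of discordant pairs with a symptom report, which the documents do not give. The 6% row corresponds, for example, to 30% with a symptom report, half of those recognised and 40% of those changed: 0.30 × 0.50 × 0.40 = 0.06. All three fractions are assumptions.

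**The case against.** The strongest reply is that the conflict is inferred. In Protocol 2.5 the symptom sentence follows the text on storage and export for tabulation, so the files meant may be the study files that hold the finished reports. Section 3 says that readers are masked to patient data, and a symptom report is arguably patient data. On that reading the two rules can coexist. This stands in part: the documents do not say when symptoms are attached. But the stated purpose is interpretation of the tracing, and no step is described that keeps the text from the readers.

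A reader might infer that the protocol's own rule defeats the blinding. The documents do not support that. They leave the timing open, and only patients who report symptoms are exposed.

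A reader might also infer that the bias always favours the test device. That is too strong. The recordings come from separate recorders, and recall cannot put an episode on a tracing that did not capture it. Only interpretive calls can be carried over. Agreement is the expected direction, not a certain one.

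Finally, a reader might infer a large inflation. With r of 20% to 30%, the model above gives success probabilities of 30.4% to 55.0% (Wald) or 16.1% to 35.9% (exact). Nothing in the documents supports r of that size across all discordant pairs.

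It is also fair to say that symptoms are only one cue. Simultaneous tracings of equal duration, with similar heart rates and ectopic counts, may be recognisable without them.

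**Conclusion.** The point holds as a gap in the masking procedure. As written, the plan allows the same physicians to see the same symptom report in both exams of a pair, while stating without qualification that pairs cannot be identified. The likely effect, confined to patients with a symptom report and to interpretive calls, is towards agreement.

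The size is unknown. At a true accuracy of 85% and n = 182, an assumed r of 6% to 10% raises the chance of success from 4.8% to between 9.1% and 13.4% (Wald), or from 1.7% to between 3.6% and 5.7% (exact). These figures show sensitivity to an assumption and do not estimate what happened. The point deserves correction because it touches the primary endpoint and the remedy is cheap.

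**What to change.** **If reading is not complete.** State in Protocol 2.5 that symptom data are withheld from the readers until the arrhythmia calls for that exam are recorded and locked, and are then added for symptom correlation. Add the same sentence to SAP 2.1. The same physicians can do both steps.

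**If reading is complete.** This is plausible: the Protocol section 7 schedule ends data collection in November 2021, and version 4.0 is dated 25 February 2022. In that case:
- In Protocol section 3 and SAP 2.1, replace the claim of impossibility with an accurate account of what the readers saw and when.
- Report the limitation.
- Add to SAP 5.4 a supportive table of primary accuracy and kappa by presence of a symptom report.

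**Cost and limits.** The locked call means slightly more handling per exam. It removes one cue only. For the table, symptom status may have to be extracted from the reports, since neither Protocol 4.1 nor SAP 4.5 lists it as a variable. The strata will be imprecise. At the planned accuracy of 0.911 about 182 × 0.089 = 16 pairs are discordant. With an assumed equal split (91 and 91), the 95% interval for the difference in accuracy is about ±1.96·√[0.911 × 0.089 × (1/91 + 1/91)] = ±8 percentage points. Patients with symptoms may also differ in arrhythmia mix, so the table can neither prove nor exclude recall and should be labelled accordingly.

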4.3. Secondary Endpoints

Comparison of the detection of each type of arrhythmia between the two devices

- Comparison of the duration of the examination between the two devices;
- Comparison of mean, minimum, and maximum heart rate captured between the two devices;
- Comparison of the total atrial ectopic heart beats captured between the two devices;
- Comparison of total ventricular ectopic heart beats captured between the two devices;
- Comparison of total episodes of supraventricular tachycardia, ventricular tachycardia, and pauses between the two devices;
- Evaluate the convenience of using the two registration systems.

The individual categorical secondary endpoints (detection of each type of arrhythmia) will also be evaluated by diagnostic statistics (accuracy, sensitivity, specificity, positive and negative predictive values) with respective 95% confidence intervals.

The continuous secondary endpoints (mean, minimum and maximum heart rate, total atrial and ventricular ectopic heart beats, total episodes of supraventricular tachycardia, ventricular tachycardia and pauses) will be described by Bland-Altman plots accompanied by Lin and Pearson correlation coefficients.

Lists with the patient's reports will be made to evaluate the convenience of the systems. The Chi-square test or Fisher's exact test will be used to evaluate the

proportion of patients who report greater comfort (comfort of the device) with *Quoreone* versus *Cardiolight*.

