### Secondary Outcomes

The individual categorical secondary endpoints (detection of each type of arrhythmia) will also be evaluated by diagnostic statistics (accuracy, sensitivity, specificity, positive and negative predictive values) with respective 95% confidence intervals.

The continuous secondary endpoints (mean, minimum and maximum heart rate, total atrial and ventricular ectopic heart beats, total episodes of supraventricular tachycardia, ventricular tachycardia and pauses) will be described by Bland-Altman plots accompanied by Lin and Pearson correlation coefficients.

Lists with the patients' reports will be made to evaluate the convenience of the systems. The Chi-square test or Fisher's exact test will be used to evaluate the proportion of patients who report greater comfort (comfort of the device) with *Quoreone* versus *Cardiolight*.

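### The convenience questionnaire is described for QuoreOne only, so as described it does not supply the data for the planned QuoreOne-versus-Cardiolight comfort comparison

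*Protocol*

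**What the plan says.** **Objective.** Protocol 1.4.2 states that "the duration of the examination and the convenience of using both systems should also be compared". SAP 1.2 repeats this.

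**Endpoint.** Protocol 4.3 lists as a secondary endpoint: "Evaluate the convenience of using the two registration systems". SAP 5.1 has the same item.

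**Analysis.** SAP 5.2 (Secondary Outcomes) plans two things. The first is descriptive: "Lists with the patients' reports will be made to evaluate the convenience of the systems". The second is a hypothesis test, chi-square or Fisher's exact, on the "proportion of patients who report greater comfort (comfort of the device) with *Quoreone* versus *Cardiolight". Protocol 4.3 matches.

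**Data collection.** Protocol 2.5 says that, once both devices are off, "the participant will be asked to answer a questionnaire about the convenience of use and functions of the *QuoreOne* device". SAP 2.1 likewise describes "a questionnaire about the convenience of use and functions of the *QuoreOne* device". Neither document describes any other convenience instrument.

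**Wear.** Every patient wears the two recorders simultaneously for about 24 hours (Protocol 3; SAP 2.2 and 2.6).

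**The concern.** The objective, the endpoint and the test each need information on two devices, or a direct choice between them. The instrument is described as asking about one. If the form matches its description, the planned proportion cannot be formed, because nothing records how a patient found Cardiolight or which recorder the patient preferred.

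At stake is a named secondary endpoint with a hypothesis test attached, in a study funded by QuoreOne's maker (Protocol 9). A report that QuoreOne was more comfortable would then have no comparator data behind it. The choice of test is a separate matter: even a well-chosen paired test needs a Cardiolight or preference answer to work on.

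**Working it through.** The plan gives no figure for the convenience comparison, so there is none to reproduce. The 182 patients were sized for the accuracy endpoint (SAP 2.3) and are used here only as the number of possible respondents.

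**Step 1: what the test needs and what the form is said to give.**

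| Element | Where | Devices covered |
|---|---|---|
| Objective | Protocol 1.4.2; SAP 1.2 | both |
| Endpoint | Protocol 4.3; SAP 5.1 | both |
| Test quantity | Protocol 4.3; SAP 5.2 | one versus the other |
| Lists of patient reports | Protocol 4.3; SAP 5.2 | both, source not stated |
| Questionnaire | Protocol 2.5; SAP 2.1 | QuoreOne |

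The first four rows agree with each other. The questionnaire is the row that does not match, and it does so in both documents.

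**Step 2: can a QuoreOne-only answer give the planned proportion?** The quantity is the share of patients who find QuoreOne more comfortable than Cardiolight. It needs either two ratings per patient or one stated preference. A single QuoreOne rating, apart from one at the end of its scale, is compatible with Cardiolight being rated higher, the same or lower. The share is therefore not determined by such answers, however many patients respond.

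**Step 3: does simultaneous wear block the comparison?** Suppose each of the 182 patients names the more comfortable device, with no ties (an assumption).

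- 95% half-width at 50%: 1.96 × √(0.5 × 0.5 / 182) = 0.0726, about 7.3 percentage points.
- Exact two-sided 5% sign test: the smallest count with upper tail at or below 0.025 under a true share of 50% is 105 of 182 (tail 0.0225), that is 105/182 = 57.7%.
- Power of that test: 26% at a true preference of 55%, 76% at 60%, 80% at 60.5%.

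Ties reduce the informative number. If half of the patients answered no difference (an assumption), 91 answers would remain and the half-width would be 1.96 × 0.5 / √91 = 0.103, about 10.3 points.

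A preference can therefore be estimated with useful precision under simultaneous wear, provided that the question is asked.

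**Step 4: timing.** The schedule in Protocol 7 shows data collection ending in November 2021. The protocol reviewed is version 4.0 of 25 February 2022. On that schedule, the questionnaires were completed before this version was written.

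**The case against.** The strongest reply is that a one-line description is not the form. The items are not in the documents, and a questionnaire headed as being about QuoreOne could still ask whether it was more comfortable than the conventional Holter. The test wording presupposes such an answer, and the planned lists refer to the systems in the plural. This stands. A reader might infer that no Cardiolight data exist (182 ratings against none), but the documents show only that no such item is described. They still need reconciling, because the item that feeds the endpoint is not identified anywhere.

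A reader might also infer that wearing both recorders together makes the devices inseparable. The documents do not support that. Each patient experiences both, and Step 3 shows that a within-patient preference is estimable. What remains is a caution: overall comfort during shared wear is harder to attribute to one recorder.

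The protocol's introduction mentions "the dependence on electrode cables, which often limit the mobility of patients", which may suggest that the study intends to claim better mobility. That is background. No objective, endpoint or analysis measures mobility, and the tested quantity is limited to comfort of the device. Nor do the documents support saying that a one-device form favours the device it names.

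Finally, convenience is the last-listed secondary endpoint, with no success criterion or power statement. That limits the consequence but does not remove the mismatch.

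**Conclusion.** The point holds as an inconsistency between the instrument and the endpoint. As described in both documents, the questionnaire covers QuoreOne alone and does not supply the data for the planned comparison with Cardiolight. The conclusion rests on that description being accurate. If a comparative item was used, the defect shrinks to an incorrect description in two sections.

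The effect is confined to the convenience endpoint and any comfort claim drawn from it; the primary accuracy conclusion is untouched. The plan should be corrected, but the point does not threaten the study. Simultaneous wear is a limitation on interpretation and not a second defect.

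**What to change.** 1. In Protocol 2.5 and SAP 2.1, have the questionnaire ask the same comfort items for QuoreOne and for Cardiolight, plus one neutral preference item with the options QuoreOne, Cardiolight and no difference. In SAP 5.2, name the item that defines the tested proportion.
2. If a comparative item was already in use, quote it in both sections and identify it as the source of the endpoint. No new data are then needed.
3. For patients who completed only a QuoreOne form, report the answers descriptively and make no comparative comfort claim. Given the schedule, this may be the only option left for many or all patients.
4. State as a limitation that preferences were given while both recorders were worn, which blurs the attribution of overall comfort but still allows a within-patient comparison.

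The cost is a slightly longer form if collection is still open, or a narrower comfort claim if it is closed, plus a short text change in each document. No extra visit is needed.

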#### 2.6. Moments of Evaluation of Results

The exams performed by the conventional system (*Cardiolight*, *Cardios*) and the *QuoreOne* system will be implemented at the same time in the same patient and for the same duration. The monitoring of the electrical activity of the heart during a period of approximately 24 hours will be done by the systems, which will record the records at times according to the custom of medical practice.

The parameters will be analyzed with anonymized data from the participants.

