#### 3.3. Analysis Populations

All individuals of both sexes, aged 18 years or older who use both systems simultaneously for 24 hours, present complete data in both examinations and have signed the consent form will be part of the Full Analysis Set (FAS).

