### 5.3. Missing Data

No imputation will be performed and only analysis of complete data will be performed.

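### The duration comparison is restricted to patients with 24 hours and complete data on both recorders, so the early stops and failures that would make durations differ are largely selected out

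*Protocol*

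**What the plan says.** Protocol 1.4.2 states as part of the secondary objective that "the duration of the examination and the convenience of using both systems should also be compared", and SAP 1.2 repeats this. Protocol 4.3 lists the endpoint as "Comparison of the duration of the examination between the two devices", as does SAP 5.1. Neither document says whether duration means time worn, time recorded or time with interpretable signal.

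The design sets planned duration equal. Protocol section 3 (Methodology) says: "These tests will be implemented at the same time in the same patient and for the same duration". SAP 2.1 carries the same sentence, and SAP 2.6 says that both systems "will be implemented at the same time in the same patient and for the same duration". SAP 2.6 also allows some latitude: "The monitoring of the electrical activity of the heart during a period of approximately 24 hours will be done by the systems".

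The analysis population is then narrowed. The Full Analysis Set (FAS) in SAP 3.3 consists of consenting adults "who use both systems simultaneously for 24 hours, present complete data in both examinations". SAP 5.3 adds: "No imputation will be performed and only analysis of complete data will be performed". No other analysis population is defined.

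On method, Protocol 4.3 and SAP 5.2 assign Bland-Altman plots with Lin and Pearson coefficients to a bracketed list that begins "The continuous secondary endpoints (mean, minimum and maximum heart rate, total atrial and ventricular ectopic heart beats, total episodes of supraventricular tachycardia" and ends with ventricular tachycardia and pauses. Duration is not in it. SAP 5.2 opens with a general statement that every measure from each technique will be summarised with the descriptive statistics of SAP 4.5.

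**The concern.** A comparison of duration between two recorders is informative mainly through the patients in whom one recorder ran shorter than the other. If entry to the analysis requires that both ran for the full period with complete data, the rule conditions on the outcome being compared. What remains mostly reflects the protocol's instruction to apply both devices together, and says little about how the devices performed.

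Two things are at stake. First, near-identical durations could be read as support for the comparability hypothesis (Protocol 1.3) although design and selection largely produced them. Second, the rationale in Protocol 1.2 rests partly on recording reliability: it says that cables bring interference and may force repeat exams, and that cable-free recording improved signal quality. Duration is the listed endpoint closest to that claim, and the analysis set removes most of the evidence it could supply.

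**Working it through.** The plan gives no figure for duration: no expected difference, no tolerance, no failure rate. The check is therefore mainly a comparison of the relevant sections, followed by an illustration.

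**Step 1: which differences can arise, and which survive.**

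| Meaning of duration | Can the devices differ? | What the FAS leaves |
|---|---|---|
| Time worn | Not by plan (Protocol 3; SAP 2.1, 2.6) | Close to zero |
| Time recorded | Yes: early stop, detachment or recording failure on one device | Small variation around 24 hours; large differences tend to be excluded (SAP 3.3, 5.3) |
| Time with interpretable signal | Yes, as above plus signal loss | Depends on what complete data means, which is not defined |

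Under each meaning the FAS difference is either set by the design or trimmed by selection.

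**Step 2: which analysis applies.** The methods in Protocol 4.3, SAP 5.2 and SAP 5.4 can be taken in turn. Diagnostic statistics cover detection of each arrhythmia. Bland-Altman, Lin and Pearson cover heart rates, ectopic beats and episode counts. Chi-square or Fisher covers comfort. Kappa covers the arrhythmia criteria. None covers duration. The general sentence in SAP 5.2 yields n, mean, SD, median, interquartile range, minimum and maximum per device, but no within-patient difference and no interval for one.

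**Step 3: illustration (assumed values, not from the documents).** Let a fraction f of fitted patients lose L hours on one device only, always the same device, with no loss in the others. Let k be the share of those patients that the FAS keeps.

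- Mean difference in all fitted patients: f × L.
- Mean difference in the FAS: f × k × L / (1 − f × (1 − k)).

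With f = 0.10 and L = 4 h, f × L = 0.4 h = 24 min. With f = 0.20 and L = 2 h, it is again 0.4 h = 24 min. As a share of the day, 24 / 1440 = 1.7%. In the FAS the result runs from 24 min if all such patients are kept (k = 1) down to 0 if none are (k = 0). A strict reading of SAP 3.3 puts k near 0.

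**Step 4: how many patients would be out of view.** SAP 4.3 counts its minimum of 182 in patients with complete data. If 10% of fitted patients were excluded, 182 / 0.90 ≈ 202 would be fitted and about 20 would not be seen. At 20%, 182 / 0.80 ≈ 228 would be fitted, with about 46 not seen.

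If losses occurred equally often on both devices, the mean difference would be near zero in either population. Selection would then narrow the spread of the paired differences and leave their centre unchanged.

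**The case against.** A reader might infer that the two durations cannot differ at all. The documents do not support that. Applying two recorders together for the same planned time does not fix what each one records, SAP 2.6 speaks of approximately 24 hours, no tolerance is attached to the 24 hours or to complete data in SAP 3.3, and duration itself is undefined. Some variation can remain in the FAS, and how much is unknown.

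A reader might also infer that duration has no analysis. That is too strong as well: the general sentence in SAP 5.2 gives a descriptive summary per device. What is missing is the between-device comparison that the endpoint promises.

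Nor do the documents treat equal duration as proof of comparability. SAP 2.3 ties success to overall accuracy above 85%. Within the FAS, duration has a legitimate use as a check that the planned equal duration was achieved, which matters because ectopic totals and episode counts depend on recording time. That is a reason to keep reporting it.

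The disposition tables in SAP 4.1 will show how many recruited patients had complete data, so exclusions are not hidden. They are not specified by device, however, and carry no recorded times, so they do not replace the comparison.

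Finally, time with interpretable signal would be partly a new endpoint, and no section says that either system reports it. That objection stands and limits the fix: recorded time comes first.

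**Conclusion.** The point holds in this form. The plan promises a between-device comparison of duration, equalises planned wear time, and then analyses only patients with 24 hours and complete data on both systems. Small differences can remain, but the informative ones are largely selected out, so the comparison is biased towards equality. The missing definition and the missing paired method add to this.

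The size cannot be derived from the documents. Under the assumed loss patterns, a true mean difference of 24 minutes would appear as anything from 24 minutes down to zero, according to how strictly the 24-hour and complete-data conditions are applied. The direction of bias rests on two assumptions: that shortened recordings lead to exclusion, and that they are more frequent on one device. If they are balanced, it is the spread that is understated.

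This concerns one secondary endpoint. It does not touch the primary endpoint, the 182-patient calculation or the success criterion.

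**What to change.** In Protocol 4.3 and SAP 5.1, define duration as recorded time per device in hours, or as analysable time if the exam files or platform report it.

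In SAP 5.2, name the analysis: the within-patient difference, QuoreOne minus Cardiolight, as a paired mean or median difference with 95% CI, in all patients fitted with both recorders and not only the FAS. State how a recorder that stopped early or failed enters the calculation.

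If duration is kept in the FAS only, say in the SAP that it is reported as a check that equal duration was achieved and not as evidence of comparability.

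The cost is data extraction for patients with incomplete exams. Protocol 2.5 provides for storing the Cardiolight original file and report, and the QuoreOne platform record and report, but whether these give recorded time directly is not stated. No additional patients or procedures are needed. The change alters a secondary endpoint's analysis set. The protocol version is dated February 2022 and its schedule places data collection in 2021, so the amendment should be dated and documented as made after collection, with a statement of whether duration data had been seen.
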